## **8. TRIAL OBJECTIVES**

### **8.1. Primary Objective**

- To evaluate the proportion of patients who have a modified erythroid response (mHI-E), defined as a hemoglobin increase of  $\geq 1.5$  g/dL from baseline for  $\geq 14$  days (in the absence of red blood cell [RBC] transfusions) in non-transfusion dependent patients, or, a reduction of either  $\geq 4$  units or  $\geq 50\%$  of units of RBCs transfused compared to pre-treatment in transfusion dependent patients.

### **8.2. Secondary Objectives**

- To evaluate safety and tolerability of ACE-536
- To examine rates of erythroid, neutrophil and platelet (HI-E, HI-N and HI-P) responses (International Working Group [IWG] 2006 criteria)
- To evaluate time to mHI-E and HI-E response and duration of mHI-E and HI-E response
- To evaluate frequency of RBC transfusions in transfusion dependent patients
- To examine the pharmacokinetic (PK) profile of ACE-536
- To examine other pharmacodynamic (PD) effects (e.g., iron metabolism, erythropoietin, reticulocytes, and bone biomarkers)

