## 9.2. Discussion of Study Design

The efficacy assessment based on modified IWG criteria for erythroid response (mHI-E) was selected for this study as a variation of the accepted and widely used endpoint for the evaluation of therapies in patients with MDS, appropriate for short-term studies. This was selected as the primary endpoint due to the unknown optimal dosing interval for ACE-536 to produce a sustained response and the desire to identify the minimal safe dose level producing any erythroid response. The standard HI-E criteria for response will be evaluated as a secondary endpoint.

The initial dose level of 0.125 mg/kg is less than the maximum dose administered in the phase 1 study A536-02 of 0.25 mg/kg, which was safe and well tolerated, and produced a hemoglobin response in healthy volunteers. The safety measurements are standard for studies with investigational medications. An open-label study, conducted in a limited number of patients, with protocol-specified definitions of dose-limiting toxicity, and with protocol-specified procedures for dose escalation and reduction is considered appropriate for a proof-of-concept study in this target patient population. Dose escalation in sequential cohorts is designed to minimize the risk of excessive erythroid response and hypertension that may result from a robust response to high drug levels. Individualization of dose level in the expansion cohorts, using dose titration rules based on hemoglobin response and dose reduction rules based on safety information will maximize the proportion of patients having an erythroid response while maintaining safety.

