### 15.2.3. Secondary Analysis

**Safety analysis:** To assess clinical safety, adverse events, vital sign measurements and clinical laboratory information will be summarized. Adverse Events will be coded using the Medical Dictionary for Regulatory Activities (MedDRA). Changes from baseline for clinical laboratory values and vital signs will be summarized over time. Descriptive statistics and shift tables will be generated as appropriate.

**Secondary efficacy/pharmacodynamic analysis** of the study will be performed using the ITT and EE populations and will include:

- Modified erythroid response (mHI-E), as described above for primary endpoint, performed using the ITT population.
- HI-E response rate as defined by IWG 2006 criteria ([Appendix 5](#)). Improvements must last  $\geq$  8 weeks. For non-transfusion dependent patients, an increase of  $\geq 1.5$  g/dL from pre-treatment hemoglobin. For transfused patients, a reduction by  $\geq 4$  units of RBCs transfused (for a hemoglobin  $\leq 9.0$  g/dL) during any 8-week period on study, compared with the 8-week period prior to Cycle 1 Day 1.
- Time to mHI-E and HI-E response and duration of mHI-E and HI-E response as per the IWG 2006 criteria.
- Frequency of RBC transfusion, and rate of RBC transfusion independence in transfusion dependent patients.
- Other pharmacodynamic (PD) endpoints including:
  - Biomarkers for iron metabolism
  - Biomarkers for bone metabolism
  - Relationship of biomarkers to response
  - Rates of HI-N and HI-P

**Exploratory endpoints** will include:

- Evaluation of biomarkers related to the TGF $\beta$  superfamily.
- Evaluation of self-reported quality of life in the expansion cohort using tools including but not limited to the FACT-An questionnaire.

All binary endpoints will be summarized using both a point estimate and its exact confidence interval based on the binomial distribution. The time-to-event type secondary endpoints will be analyzed using Kaplan-Meier method to estimate the survival curve and median time to event and 95% confidence interval.

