2. STUDY OBJECTIVES

Primary Objective:

- To evaluate the proportion of patients who have a modified erythroid response (mHI-E), defined as a hemoglobin increase of ≥ 1.5 g/dL from baseline for ≥ 14 days (in the absence of red blood cell [RBC] transfusions) in low transfusion burden patients, or, a reduction of either ≥ 4 units or $\geq 50\%$ of units of RBCs transfused compared to pre-treatment in high transfusion burden patients.

Secondary Objectives:

- To evaluate safety and tolerability of luspatercept (ACE-536)
- To examine rates of erythroid, neutrophil and platelet (HI-E, HI-N and HI-P) responses (International Working Group [IWG] 2006 criteria¹. See Appendix 3)
- To evaluate time to HI-E response and duration of HI-E response
- To evaluate frequency of RBC transfusions in high transfusion burden patients
- To examine the pharmacokinetic (PK) profile of luspatercept
- To examine other pharmacodynamic (PD) effects (e.g., iron metabolism, erythropoietin, reticulocytes, and bone biomarkers)

Exploratory Objectives:

- To evaluate biomarkers related to the TGF- β superfamily
- Evaluation of self-reported quality of life in the expansion cohort using tools including but not limited to the Functional Assessment of Cancer Therapy-Anemia Scale (FACT-An) questionnaire

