5.7.1. Primary Efficacy Endpoint

The primary efficacy endpoint is the modified erythroid response (mHI-E), defined as below:

- For low transfusion burden (LTB) patients, a hemoglobin increase of ≥ 1.5 g/dL from baseline for ≥ 14 days (in the absence of RBC transfusions). Hemoglobin measurements within 7 days following RBC transfusion will be excluded from analysis.
- For high transfusion burden (HTB) patients, a ≥ 4 units or $\geq 50\%$ reduction in RBC transfusion burden during any rolling 8-week window on treatment compared to baseline. The rolling 8-week window starts on Day 1 and increments by 1 day, e.g., from day 1 to day 56, day 2 to day 57, day 3 to day 58, etc.

A point estimate of the proportion of patients achieving a modified erythroid response will be presented along with its associated exact 95% confidence interval (CI) based on binomial distribution for LTB and HTB patients separately. The complete hemoglobin measurements and RBC transfusion records will be listed for each patient.

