5.7.2.4. Time to and Duration of HI-E Response

Time to and duration of HI-E response will be analyzed for HI-E responders only.

Time to HI-E response will be defined as the time from the first dose date to the first date of any rolling 8-week window achieving HI-E response.

Duration of HI-E response will be defined as below for LTB and HTB patients, respectively:

- a. For LTB patients, duration of HI-E response will be calculated as the longest interval during which all hemoglobin measurements having increase of ≥ 1.5 g/dL from baseline.
- b. For HTB patients, duration of HI-E response will be calculated as the time from the starting date of the first rolling 8-week window achieving response to the last date of the consecutive rolling 8-week window achieving response. When there are multiple disjoint intervals with response, the longest interval will be used.

Patients with response ongoing at the last record date will be censored. Both time to and duration of HI-E response will be analyzed as continuous variables and summarized by descriptive statistics. In addition, duration of HI-E response will also be analyzed as a time to event endpoint. The survival curves will be estimated using Kaplan-Meier method if the number of patients is more than 5.

The derivations of time to and duration of mHI-E (or HI-E) response will be listed for each patient.

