5.15. Changes in Conduct or Planned Analyses from the Protocol

Major changes between SAP and the planned analysis in Protocol Amendment 6 are described below:

Item	Difference between Protocol and SAP
NTD/TD	In SAP, the terms LTB/HTB are used in place of NTD/TD in protocol.
Secondary objectives: time to and duration of mHI-E	The secondary endpoints time to and duration of mHI-E will not be analyzed.
Efficacy Evaluable Population (EE)	Analysis on Efficacy Evaluable population will not be performed. All analyses are on ITT population
Definition of baseline hemoglobin	Protocol definition: Baseline hemoglobin will be the average of at least two measures (not influenced by transfusion within 7 days of measurement); one measure performed within one day prior to Cycle 1 Day 1 and the other performed 7-28 days prior to Cycle 1 Day 1. This definition is revised in this SAP to reflect the derivation rule implemented for this study.

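### The SAP drops the summaries of time to and duration of mHI-E without a reason, so low transfusion burden patients whose primary response lasts under 8 weeks get no duration summary

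*Protocol*

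**What the plan says.** Protocol section 8.2 lists the objective "To evaluate time to mHI-E and HI-E response and duration of mHI-E and HI-E response". Section 15.2.3 carries it into the planned secondary analyses, "Time to mHI-E and HI-E response and duration of mHI-E and HI-E response as per the IWG 2006 criteria", and assigns Kaplan-Meier estimation to time-to-event secondary endpoints.

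SAP section 2 shortens the objective to "To evaluate time to HI-E response and duration of HI-E response". The table of changes in SAP 5.15 says "The secondary endpoints time to and duration of mHI-E will not be analyzed". That row gives no reason, whereas the baseline-hemoglobin row of the same table says what prompted its change.

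SAP 5.7.2.4 states "Time to and duration of HI-E response will be analyzed for HI-E responders only", defines time and duration for HI-E alone, and then ends with "The derivations of time to and duration of mHI-E (or HI-E) response will be listed for each patient".

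SAP 5.15 describes differences from Protocol Amendment 6. The protocol supplied has no expansion cohort 3 and so appears to predate that amendment, but the 5.15 row itself shows that Amendment 6 still carried the mHI-E endpoints.

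**The concern.** How long the primary response lasts is tied to the reason for choosing mHI-E. Of that choice, protocol section 9.2 says "This was selected as the primary endpoint due to the unknown optimal dosing interval for ACE-536 to produce a sustained response". The SAP keeps the mHI-E rate and removes the only planned summary of how soon that response starts and how long it holds.

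The remaining summary describes a different set of patients. An LTB patient whose hemoglobin response lasts, say, 30 days counts as a success in the primary endpoint and appears in no time or duration table. A reader who takes the HI-E duration as the durability of the primary response will think it longer than it is.

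The SAP also disagrees with itself. Section 5.15 takes mHI-E time and duration out of the analysis, while 5.7.2.4 lists derived values for which no rule is written.

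**Working it through.** The plan states no figure to reproduce. The check compares the two definitions by stratum and then sizes the effect under stated assumptions.

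**Definitions (SAP 5.7.1, 5.7.2.2 and Appendix 3)**

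| Stratum | mHI-E | HI-E |
|---|---|---|
| LTB | Hemoglobin up by at least 1.5 g/dL for at least 14 days, no transfusion | Same rise over at least 8 weeks (56 days), no transfusion |
| HTB | At least 4 units or at least 50% fewer, any rolling 8-week window | At least 4 units fewer, any rolling 8-week window |

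**LTB: who is left out, and by how much the median shifts**

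Assumptions (not trial data): mHI-E duration is 14 days plus an exponential, with median M over all LTB mHI-E responders. HI-E is taken to require every value in the 8 weeks to qualify.

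- Exponential mean: τ = (M − 14)/ln 2
- Share reaching 56 days: exp(−42/τ); share left out: 1 − exp(−42/τ)
- Median among those reaching 56 days, no censoring: 56 + τ·ln 2 = M + 42

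SAP 5.7 ends efficacy derivation at the last dose plus 56 days or the last transfusion record, whichever is earlier. With a last dose on Day 85 the latest cut-off is Day 85 + 56 = Day 141. A simulation added this cut-off, with response onset assumed uniform on Days 8 to 64, and took medians of the observed durations.

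| M (days) | τ | Reach 56 days | Left out | HI-E median, no censoring | Observed medians with cut-off, mHI-E vs HI-E | Observed gap |
|---|---|---|---|---|---|---|
| 28 | 20.2 | 12.5% | 88% | 70 | 28.0 vs 70.1 | 42 |
| 42 | 40.4 | 35.4% | 65% | 84 | 42.0 vs 81.0 | 39 |
| 56 | 60.6 | 50.0% | 50% | 98 | 56.0 vs 86.6 | 31 |
| 84 | 101.0 | 66.0% | 34% | 126 | 79.5 vs 92.7 | 13 |

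The uncensored gap is 42 days in every row. It is what Kaplan-Meier estimates aim at. The plain descriptive summaries that 5.7.2.4 also plans would behave more like the last column: a 126-day response can be seen in full only if it starts by Day 141 − 126 = Day 15.

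**HTB: where the criteria differ**

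For baseline b units, HI-E allows at most b − 4 remaining units. mHI-E allows the larger of b − 4 and the whole number of units not above b/2.

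| Baseline units | mHI-E allows at most | HI-E allows at most |
|---|---|---|
| 4 | 2 | 0 |
| 5 | 2 | 1 |
| 6 | 3 | 2 |
| 7 | 3 | 3 |
| 8 | 4 | 4 |

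From 7 units up the criteria coincide. HTB starts at 4 units, and SAP 3.1 caps cohorts 2B and 3 at 6 units, so every HTB patient in those cohorts lies in the range where they differ. The window is 8 weeks under both, so the difference is in the size of the reduction and not its length.

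**The case against.** Much can be said for the SAP. Protocol 15.5 requires departures to be indicated in the SAP, and 5.15 does so. No hypothesis is tested, and the primary response rate is untouched. The mHI-E and HI-E rates are both reported by stratum, so a reader can see how many patients meet the 8-week criterion. SAP 5.7.2.1 gives a Kaplan-Meier analysis of transfusion-independence duration, and 5.7.2.9 reports the proportion of LTB patients holding a 1.0 g/dL rise for 8 weeks. Protocol 9.2 gives a second reason for mHI-E, finding the lowest safe dose with any erythroid effect, and names standard HI-E as the secondary endpoint. The duration table is labelled HI-E.

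These points limit the concern but do not remove it. The transfusion-independence analysis covers only patients with at least 2 baseline units and itself requires more than 8 weeks; the 1.0 g/dL item is a proportion, also at 8 weeks. None describes shorter primary responses.

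One objection stands as a caveat. SAP 5.7.2.2 does not say whether LTB HI-E needs every hemoglobin value or the 8-week mean to qualify, and 5.7.2.3 uses means for platelets and neutrophils. Duration in 5.7.2.4 requires all values to qualify. If HI-E rests on a mean, an HI-E responder's duration could be below 56 days and the table above would not apply as it stands.

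Four stronger readings are tempting and are not supported:

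- That mHI-E durability goes unreported. The drop is declared and a patient listing is promised; it is not summarised or analysed.
- That HI-E duration is selected for length in all patients. This holds for LTB only.
- That the overstatement is always 42 days. That ignores the SAP's own cut-off.
- That the endpoint was dropped because of the data. The trial is open-label and the SAP already records 9 treated patients in cohort 3, but nothing in the documents shows that results prompted the change.

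**Conclusion.** The concern holds in a limited form. A protocol secondary objective and its planned analysis are removed without a reason, and SAP 5.7.2.4 and 5.15 must be reconciled.

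For LTB patients, primary responses shorter than 8 weeks have no time or duration summary. Under the assumed distribution, about 88%, 65%, 50% or 34% of LTB primary responders are left out at true medians of 28, 42, 56 or 84 days. The HI-E median exceeds the mHI-E median by 42 days without censoring, or by about 42, 39, 31 or 13 days in observed durations with the Day 141 cut-off. These figures rest on the exponential form, the uniform onset and the every-value reading of HI-E. The direction under that reading follows from the definitions alone.

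For HTB patients the omission is confined to responders by the 50% route with 4 to 6 baseline units.

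**What to change.** 1. Delete the mHI-E row in SAP 5.15 and restore mHI-E in the time and duration objective in SAP section 2.
2. In SAP 5.7.2.4 apply the existing HI-E rules to mHI-E: time from first dose to the start of the first qualifying interval; duration as the longest qualifying interval; ongoing responses censored; descriptive and Kaplan-Meier summaries for all mHI-E responders, by LTB and HTB. This also supplies the rule that the promised listing lacks.
3. Keep the HI-E analysis beside it, labelled as conditional on meeting the 8-week criterion.
4. State in SAP 5.7.2.2 whether LTB HI-E requires every value or the mean to reach 1.5 g/dL.

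The cost is SAP wording and two more tables, from data already collected. The reported median duration will probably be shorter than the HI-E figure alone.

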### **8.3. Exploratory Objective**

- To evaluate biomarkers related to the TGF $\beta$  superfamily
- Evaluation of self-reported quality of life in the expansion cohort using tools including but not limited to the FACT-An questionnaire

## 9. OVERALL STUDY DESIGN AND PLAN: DESCRIPTION

This is a phase 2, open-label, multiple ascending dose study to evaluate the effects of ACE-536 on anemia in patients with low or intermediate-1 risk MDS who are not currently receiving treatment with an erythropoiesis-stimulating agent (ESA).

### 9.1. Study Design

Patients who meet the study eligibility criteria will be enrolled within 28 days of screening. Patients in all cohorts will receive ACE-536, administered subcutaneously (SC), every 3 weeks for up to 5 cycles. Dose delay(s) and dose reduction(s) may be required for individual patients as outlined in the Patient Dose Modification Rules ([Section 10.8.1](#)).

Each dose escalation cohort will consist of a minimum of 3 patients. The dose level of ACE-536 for the first cohort will be 0.125 mg/kg and the dose level(s) for subsequent cohort(s) will follow a modified Fibonacci dose escalation scheme with a maximum dose level of 0.25 mg/kg for cohort 2, 0.50 mg/kg for cohort 3, 0.75 mg/kg for cohort 4, 1.0 mg/kg for cohort 5, 1.33 mg/kg for cohort 6, 1.75 mg/kg for cohort 7, and a maximum dose level not to exceed 1.75 mg/kg. Once a minimum of 3 patients in a cohort have completed Study Day 29, the Safety Review Team (SRT) will review preliminary safety and hematologic response data and make recommendations to the Sponsor regarding whether or not to enroll an additional 3 patients in that cohort, enroll a new cohort at a higher or lower dose, or proceed to expansion cohort 1.

Expansion cohort 1 (n= approximately 30) will be treated with ACE-536 at a starting dose level of 1.0 mg/kg. Expansion cohort 1 will consist of a minimum of 10 patients who are transfusion dependent (TD) and 10 patients who are non-transfusion dependent (NTD), if feasible.

Expansion cohort 2 will be treated with ACE-536 at a starting dose level of 1.0 mg/kg. Expansion cohort 2 will be divided into two groups designated expansion cohort 2A and 2B. The targeted accrual for each group will be 25 eligible and evaluable patients but permitted to range from 22 to 28 for administrative reasons. The maximum number of patients treated will be 56.

- Expansion cohort 2A: NTD patients with  $\geq 15\%$  ring sideroblasts in the bone marrow (RS+), less than 4 weeks of exposure to erythropoietin stimulating agents (ESAs) and serum erythropoietin (EPO) level  $\leq 200$  U/L at screening.
- Expansion cohort 2B: Patients with  $< 15\%$  ring sideroblasts in the bone marrow (RS-) and  $\leq 6$  RBC units in 8 weeks prior to C1D1. This group will consist of a minimum of 10 patients who have less than 4 weeks of exposure to ESAs and 5 patients who have received  $\geq 4$  weeks of treatment with ESAs.

In the expansion cohorts, a patient's dose level may be titrated based on criteria listed in [Section 10.8.2](#), Expansion Cohorts Patient Dose Titration. The maximum dose level given to a patient will not exceed the maximum dose level evaluated in the dose escalation cohorts. Patients in the expansion cohort will be treated with up to 5 doses of ACE-536 administered once every 3 weeks.

**Table 2: Dose Escalation**

Cohort a	ACE-536 Dose Level b (mg/kg)	Number of Patients
1	0.125	3-6
2	0.25	3-6
3	0.50	3-6
4	0.75	3-6
5	1.0	3-6
6	1.33	3-6
7	1.75	3-6
Expansion 1	1.0	30
Expansion 2	1.0	up to 56
Planned Total:		up to 128

a Cohort escalation is based on SRT review and recommendation to enroll additional cohorts and/or the expansion cohort.

b The ACE-536 dose level for cohort 1 is 0.125 mg/kg. The dose level indicated for all subsequent dose escalation cohorts is the maximum dose level that can be recommended by the SRT for escalation per the modified Fibonacci dose escalation scheme. Dose escalation will not exceed 1.75 mg/kg.

## 9.2. Discussion of Study Design

The efficacy assessment based on modified IWG criteria for erythroid response (mHI-E) was selected for this study as a variation of the accepted and widely used endpoint for the evaluation of therapies in patients with MDS, appropriate for short-term studies. This was selected as the primary endpoint due to the unknown optimal dosing interval for ACE-536 to produce a sustained response and the desire to identify the minimal safe dose level producing any erythroid response. The standard HI-E criteria for response will be evaluated as a secondary endpoint.

The initial dose level of 0.125 mg/kg is less than the maximum dose administered in the phase 1 study A536-02 of 0.25 mg/kg, which was safe and well tolerated, and produced a hemoglobin response in healthy volunteers. The safety measurements are standard for studies with investigational medications. An open-label study, conducted in a limited number of patients, with protocol-specified definitions of dose-limiting toxicity, and with protocol-specified procedures for dose escalation and reduction is considered appropriate for a proof-of-concept study in this target patient population. Dose escalation in sequential cohorts is designed to minimize the risk of excessive erythroid response and hypertension that may result from a robust response to high drug levels. Individualization of dose level in the expansion cohorts, using dose titration rules based on hemoglobin response and dose reduction rules based on safety information will maximize the proportion of patients having an erythroid response while maintaining safety.

## 9.3. Selection of Study Population

### 9.3.1. Inclusion Criteria

Eligible patients must meet **all** of the following criteria:

1. Men or women  $\geq$  18 years of age.
2. Documented diagnosis of idiopathic/de novo MDS or non-proliferative chronic myelomonocytic leukemia (CMML) according to WHO criteria (white blood count [WBC]  $<$  13,000/ $\mu$ L) that meets IPSS classification ([Appendix 2](#)) of low or intermediate-1 risk disease as determined by the microscopic and standard cytogenetic analyses of the bone marrow and peripheral complete blood count (CBC) obtained during screening.
3. Anemia defined as:
  - Mean hemoglobin concentration  $<$  10.0 g/dL of 2 measurements (one performed within one day prior to Cycle 1 Day 1 and the other performed 7-28 days prior to Cycle 1 Day 1, not influenced by RBC transfusion within 7 days of measurement) for non-transfusion dependent patients (defined as having received  $<$  4 units of RBCs within 8 weeks prior to Cycle 1 Day 1) (Participation in all cohorts), OR
  - Transfusion dependent, defined as having received  $\geq$  4 units of RBCs within 8 weeks prior to Cycle 1 Day 1 (transfusion dependent patients are allowed in dose escalation cohorts and expansion cohort 1 only; patients with  $\leq$  6 units of RBCs within 8 weeks prior to Cycle 1 Day 1 may be allowed in cohort 2B).
4. Serum erythropoietin levels and prior erythropoiesis-stimulating agent (ESA) treatment:
  - Dose escalation cohorts and expansion cohort 1 patients: Serum erythropoietin level  $>$  500 U/L, OR, if  $\leq$  500 U/L, patient is non-responsive, refractory, or intolerant to erythropoiesis-stimulating agents (ESAs), or ESAs are contraindicated or unavailable.
  - Expansion cohort 2 patients: If patient is RS+ (defined as having  $\geq$  15% ring sideroblasts in the bone marrow), has less than 4 weeks' exposure to ESAs and serum erythropoietin level  $\leq$  200 U/L. If a patient is RS- (defined as having  $<$  15% ring sideroblasts in the bone marrow), prior ESA treatment and any serum erythropoietin level is allowed
5. No alternative treatment options, per national MDS guidelines, are available and/or appropriate for the patient, at the discretion of the investigator.
6. ECOG performance status of 0, 1, or 2 (if related to anemia).
7. Adequate renal (creatinine  $\leq$  2.0 x upper limit of normal [ULN]) and hepatic (total bilirubin  $<$  2 x ULN and AST and ALT  $<$  3 x ULN) function.

8. Adequate transferrin saturation ( $\geq 15\%$ ), ferritin ( $\geq 50 \mu\text{g/L}$ ), folate ( $\geq 4.5 \text{ nmol/L}$  [ $\geq 2.0 \mu\text{g/L}$ ]) and vitamin B12 ( $\geq 148 \text{ pmol/L}$  [ $\geq 200 \text{ pg/mL}$ ]) during screening (supplementation and retest during screening is acceptable).
9. Females of child bearing potential (defined as sexually mature women who have not undergone hysterectomy or bilateral oophorectomy, or are not naturally postmenopausal  $\geq 24$  consecutive months) must have negative urine or blood pregnancy test prior to enrollment and use adequate birth control methods (abstinence, oral contraceptives, barrier method with spermicide, or surgical sterilization) during study participation and for 12 weeks following the last dose of ACE-536. Males must agree to use a latex condom during any sexual contact with females of child-bearing potential while participating in the study and for 12 weeks following the last dose of ACE-536, even if he has undergone a successful vasectomy. Patients must be counseled concerning measures to be used to prevent pregnancy and potential toxicities prior to the first dose of ACE-536.
10. Patients are able to adhere to the study visit schedule, understand and comply with all protocol requirements.
11. Patient understands and is able to provide written informed consent.

